excluded if their ETG levels are negative.. The Clinical Institute Withdrawal Assessment (CIWA-Ar) will be used to facilitate assessment of withdrawal, and decisions regarding appropriateness for study entry with respect to physical dependence will be made based on the judgment of study physicians using a the CIWA-Ar score of 10 for an approximate cutoff level. All our study physicians have extensive experience in assessing and triaging patients with alcohol withdrawal. Subjects that need detoxification will be referred for detoxification, and may be eligible to begin the study following successful completion of detoxification.

6.D. Study Periods:

6.D.1. Visit 0 (Screening Visit): At screening visits, subjects are asked to provide informed consent and a screening number will be assigned. A medical and psychiatric history obtained from subjects. Drinking data for the 7 days prior to the screening visit will be collected via the Timeline Follow-Back (TLFB) Method. Blood and urine samples are taken for routine clinical laboratory evaluations (complete blood count, serum chemistry panel, urinalysis, gamma-glutamyltransferase (GGT) concentration), and screening for drugs of abuse, and pregnancy testing (in all females of reproductive potential) will occur. If no medical problems are identified that would limit the subject's participation, he/she will be administered the Structured Clinical Interview for DSM-IV (SCID-I) to identify current and lifetime psychiatric disorders. Either at the screening visit, or between the screening and baseline visit, a physician or nurse practitioner will do a complete medical history and physical on the subject. Alternatively, if subjects have had a complete medical physical completed at the VA within the last 30 days (for example, by their primary care doctor), we will use that exam to qualify them for the study.

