6.D.2. Visit 1 (Baseline Visit): N= 160 subjects will be randomly assigned to receive either ZNS (80 subjects) or placebo (80 subjects). We will use blocked stratified randomization with treatment site (VA Connecticut versus Bedford) and the use of other psychotropic medications (e.g., antidepressants) as the stratification variables, with block sizes of 4 in each stratum to achieve treatment balance throughout the randomization process. Within 21 days after the screening visit, eligible subjects undergo a two-hour pre-treatment assessment (described below). At the baseline visit, subjects will complete a packet of questionnaires. Subjects will receive their first medication management session and first supply of study medication during a treatment session (visit 1) scheduled on the same day, following completion of the baseline assessments.

Subjects will begin study medication (i.e., ZNS or matching placebo) at an initial dosage of 100mg/day. All subjects will be asked to bring any remaining capsules and the study medication container to their next and all subsequent clinic visits, so that capsule counts can be used to measure compliance. The subject begins 6-week titration phase, during which the dosage will be titrated up as indicated above and in Table 1. Subjects will be paid a nominal but fair amount of money in compensation for all visits, including follow-up visits. Table 1 shows the titration schedule:

TABLE 1: Medication Titration Schedule

Week	Placebo	Zonisamide dose
1	One capsule daily	100mg QHS
2	Two capsules daily	200mg QHS
3	Two capsules daily	200mg QHS
4	Three capsules daily	300mg QHS
5	Three capsules daily	300mg QHS
6	Four capsules daily	400mg QHS
7	Four capsules daily	400mg QHS
8-9	Five capsules daily	500mg QHS (Target dose)
10-16	Five or Six capsules daily, 7 weeks duration	Continue 500mg daily or optional increase to 600mg QHS, 7 weeks duration
17-18	TAPER: Decrease capsules by one a day every 3 days, over a period of up to 15 days	TAPER: Decrease dose 100mg every 3 days, over a period of up to 15 days

Table 1 notes: 7 weeks of titration to the 500mg daily target dose. 9 weeks at the target dose with the option to increase to 600mg daily after two weeks at target if treatment response is suboptimal and there are no significant side effects (no current moderate to severe AE's with 500mg daily).

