6.F.1. Laboratory/Medical Assessments. The purposes of these assessments are: 1) to screen subjects for medical exclusion criteria, 2) to monitor medication adherence (retrospectively), 3) to assess potential side effects of medication, and 4) as objective measures of drinking. Prior to entrance into the study, each subject will receive a physical examination, urinalysis and urine toxicology, urine Ethyl glucuronide, CBC, and a chemistry panel (which includes electrolytes, liver enzymes, bilirubin, creatinine, and BUN). Women of childbearing potential will undergo serum pregnancy testing prior to beginning treatment and then urine pregnancy testing monthly thereafter (i.e., every 4 weeks) to identify women who become pregnant, so as to avoid exposing the fetus to the study medication. After 4 weeks on medication, and at the study midpoint (after treatment week 8) and at the end of the 16-week treatment phase, serum chemistry (including bicarbonate level), liver function tests, CBC, and serum GGT will be repeated. In order to monitor possible medication side effects, weight and vital signs (blood pressure and pulse) will be obtained at each treatment visit. Urine drug screens will be obtained at the initiation of the study to identify individuals who use drugs regularly, and will be repeated weekly thereafter. General metabolic and hematologic labs will be drawn more frequently if needed in order to monitor the health of subjects during the study. We will obtain blood phosphatidylethanol (PEth) levels at baseline, and weeks 8, 12 and 16 and urine Ethyl Glucuronide (EtG) levels at screening and weeks 4, 8, 12, 16, to use as biomarkers of alcohol use.

Table 2: Schedule of Assessments (See Table 3 for Stress Lab Assessments)

	SC	BL	Study Week																
			1	2	3	4	5	6	7	8	9	10	11	12	13	14	15	16	18
Surveys/Procedures																			
Overview and Consent	X																		
Demographics	X																		
Locator Information	X																		
SCID-IV	X																		
Medical History/ Physical/Psych Exam	X																		
AUQ		X	X	X	X	X	X	X	X	X	X	X	X	X	X	X	X	X	X
BDI		X	X	X	X	X	X	X	X	X	X	X	X	X	X	X	X	X	X
CIWA	X	X	X	X	X	X	X	X	X	X	X	X	X	X	X	X	X	X	X
C-SSRS		X	X	X	X	X	X	X	X	X	X	X	X	X	X	X	X	X	X
PCL-5		X	X	X	X	X	X	X	X	X	X	X	X	X	X	X	X	X	X
SAFTEE		X	X	X	X	X	X	X	X	X	X	X	X	X	X	X	X	X	X
STAI		X	X	X	X	X	X	X	X	X	X	X	X	X	X	X	X	X	X
TLFB/measures of treatment received	X	X	X	X	X	X	X	X	X	X	X	X	X	X	X	X	X	X	X
MM		X	X	X	X	X	X	X	X	X	X	X	X	X	X	X	X	X	X

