We will use the percentage of subjects with no heavy drinking days (**PSNHDD**) as the primary outcome variable. This outcome is the FDA recommended endpoint for pivotal trials, and is described in Falk et al., (2010). The PSNHDD can be derived from each subject's TLFB data. An important initial consideration in considering effectiveness will be to identify baseline differences between groups that may have occurred despite randomization. **Successful outcomes during the treatment trial will be defined in terms of a statistically significant difference on the primary outcome measure: PSNHDD, compared during the 8 weeks of active treatment at the target dose, allowing for a 6 week grace period for the medication titration.** For all analyses, heavy drinking days will be defined as follows; for men > 5 drinks in a day and for women > 4 drinks in a day. Patients will be followed irrespective of whether they continue to receive medication treatment, so that analysis will include all data available for the 8-week treatment period. The analysis will be **intent-to-treat**, and dropouts will be considered as having relapsed to heavy drinking. We will use a logistic regression analysis with PSNHDD as a categorical dependent variable. Medication condition (placebo or ZNS) will be the main independent variable, and we will include the variables of early onset of alcoholism (EOA, binary), and the use of additional psychotropics (e.g., antidepressants, a binary variable) as covariates. The α will be set at .05 for the primary outcome variable. Between site differences will be explored.

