6.I.7. Pharmacogenetic Data Analyses and Power Estimate (Exploratory Specific Aim 4): We will explore the interaction of the DBH SNP and ZNS described in section B.3.e, in terms of treatment response using mixed models or logistic regression where appropriate. With an N=160 we should be well powered to detect an effect of the DBH SNP, based on our previous study, from which we calculated an OR of approximately 12.6 for those on naltrexone with the advantageous allele (Cohen's d = 1.4). Given the large effect size observed, albeit from one small study, we should be well powered (> .99) to find a significant pharmacogenetic interaction if it exists on PSNHDD or secondary outcomes. Using the more conservative effect size from the Wald chi square logistic regression model for the DBH genotype-naltrexone interaction, (Cohen's d = .5), we should be well powered (>.99) to find a similar interaction for ZNS. Given the exploratory nature of the pharmacogenetic analyses, they will not be corrected for multiple comparisons. Estimates of effect sizes will be used for replication of the findings in appropriately powered future studies.

6.J. Timeline For Recruitment And Other Study Objectives: As shown in Table 4, recruitment will take place over 45 months, requiring enrollment of approximately 40 total patients per year (or approximately 2 patients/month at each site).

Table 4: Timeline of Performance Goals

Activity	Year 1	Year 2	Year 3	Year 4	Year 5
Staff training & study preparation					
Patient enrollment					
Endpoint assessments					
3-month follow-ups					
Data entry & cleaning					
Data analysis					
Report writing					

6.K. Plan For Managing And Integrating The Two Clinical Sites: This project will take place at two sites: the West Haven VAMC (VA Connecticut Health System) and the Bedford VAMC (both of which are in VISN1). The principal investigator ([name].) and Bedford site investigator ([name].) have agreed to engage in this collaborative effort, each bringing expertise in alcohol research that will be synergistic. Working together, the partnering sites will operate via a steering committee that will ensure the integrity of the research plan with an emphasis on safety, adherence to the protocol, and the integrity of the data and its analysis. The researchers will build upon the existing relationship between the investigative groups that has resulted in a successful collaboration for more than ten years.

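### One fixed block size of 4, printed in the protocol, leaves a modest and avoidable way to guess assignments if blinding is imperfect

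*Combined protocol and SAP*

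**What the plan says.** Section 6.D.2 plans 1:1 allocation of 160 patients by blocked stratified randomisation. The factors are "treatment site (VA Connecticut versus Bedford) and the use of other psychotropic medications (e.g., antidepressants) as the stratification variables". A single block length then applies to every cell that these factors form: "with block sizes of 4 in each stratum to achieve treatment balance throughout the randomization process". Section 6.I.2 treats the second factor as binary ("the use of additional psychotropics (e.g., antidepressants, a binary variable) as covariates"), so there are four strata. No other block size and no random variation of size is described. The documents do not say who generates or holds the list, or whether the block size is withheld from clinical staff.

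Section 6.J sets recruitment at 45 months, "approximately 2 patients/month at each site".

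Section 6.C leaves room for judgement at entry. Criterion (k) lets investigators exclude anyone they consider clinically unsuitable. Criterion (l) depends on physicians' view of the need for detoxification. On withdrawal, "decisions regarding appropriateness for study entry with respect to physical dependence will be made based on the judgment of study physicians", with a CIWA-Ar score of 10 as an approximate cutoff only.

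The trial is double blind with matching placebo capsules that follow the same titration (Section 6.D.2, Table 1).

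**The concern.** In a block of known length, each arm that staff can infer narrows what comes next. Whoever decides on a borderline candidate could then be influenced, knowingly or not, by the likely next arm. Matching capsules protect against this only as long as arms cannot be read from what staff observe.

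The documents name several possible cues:
- Weight is taken at every treatment visit (Section 6.F.1), and weight loss is described as a zonisamide effect (Sections 4.A and 4.A.3).
- Staff go through a weekly checklist built from known zonisamide side effects (Section 6.F.2(b)), and the pilot showed an excess of gastrointestinal events (Section 8.B).
- After 4 weeks, at midpoint and at week 16, "serum chemistry (including bicarbonate level), liver function tests, CBC, and serum GGT will be repeated", and Section 8.B cites a metabolic acidosis warning.

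At stake is selection on prognosis. Stratification does not prevent it. The primary model, which adjusts for early onset and psychotropic use, would not remove selection on unrecorded prognosis. The masking questionnaire (Section 6.F.2(d)) is completed by subjects at endpoint, so it would not detect staff guessing at enrolment.

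**Working it through.** The plan gives no figure for predictability. Its nearest figure is power above 89% with 80 per group (Section 6.I.6). Pilot counts of 12 and 7, with 20 per arm assumed from N = 40, give 60% versus 35%. The pooled two-sided calculation gives 89.4%, which reproduces the statement. The average success rate of 47.5% is used below.

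**Speed of filling.** 160/45 = 3.6 patients a month; over 4 strata this is 0.89 per stratum per month if strata are equal. A block of 4 takes 4/0.89 = 4.5 months, or 3 to 9 months if 25% to 75% of patients use psychotropics (assumed). Treatment lasts 16 weeks. (Section 6.F.2(e) mentions three sites in passing; Sections 6.B, 6.D.2 and 6.K give two, so four strata is the right count.)

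**Upper bound: all earlier arms known.** A block holds 2 of each arm, so there are 6 equally likely orders. The chance that an assignment is forced is 0, 0, 1/3 and 1 at places 1 to 4. The share that is certain is (0 + 0 + 1/3 + 1)/4 = 33.3%, about 53 of 160 (about 52 allowing for incomplete last blocks). Best-guess accuracy by place is 1/2, 2/3, 2/3 and 1, a mean of 17/24 = 70.8%.

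Suppose there is no drug effect, and success probability is shifted by *s* in opposite directions on the certain third (*s* is assumed). Then bias = 2*s*/3. SE = √(2 × 0.475 × 0.525/80) = 0.079.
- *s* = 5 points: bias 3.3 points, type I error 7.1%.
- *s* = 10 points: bias 6.7 points, type I error 13.5%.

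**Imperfect inference.** Let each earlier arm be guessed correctly with probability *q*, independently (assumed). The chance of a correct guess is 1/2 at place 1, (1 + *q*)/3 at places 2 and 3, and *m* = *q*² + 2*q*(1 − *q*)² at place 4, where one guesses against the majority of the three earlier guesses. So hit rate = [1/2 + 2(1 + *q*)/3 + *m*]/4.

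Apply the shift where the assignment looks forced: place 3 when both earlier guesses agree, and place 4. Then bias = 2*s* × [(2*q* − 1)/3 + (2*m* − 1)]/4. Check: at *q* = 1 this returns 2*s*/3. Type I error uses the normal approximation with the SE above.

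| *q* | *m* | Hit rate | Bias in points, *s* = 5 to 10 | Type I error |
|---|---|---|---|---|
| 0.6 | 0.552 | 53% | 0.4 to 0.9 | 5.0% to 5.1% |
| 0.7 | 0.616 | 56% | 0.9 to 1.8 | 5.2% to 5.6% |
| 0.8 | 0.704 | 60% | 1.5 to 3.0 | 5.4% to 6.7% |

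At *q* = 0.5 (blinding intact) *m* = 0.5 and the bias is zero.

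**Varied, undisclosed block sizes, all earlier arms known.** These figures come from simulating lists of 40, with the guesser updating on block size and position.

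| Sizes | Certain | Best guess right | Worst imbalance in a stratum |
|---|---|---|---|
| 4 | 33.3% | 70.8% | 2 |
| 4, 6 | 5.6% | 69% | 3 |
| 4, 6, 8 | 2.3% | 68% | 4 |

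**The case against.** The strongest reply is that the one-third figure applies only when blinding has already failed, and that the cues in the documents are weak. Section 8.B calls metabolic acidosis rare, so bicarbonate cannot mark arms in general. The largest adverse-event gap it lists is somnolence, 17% versus 7%. Used alone, that identifies an arm correctly 0.5 + 0.10/2 = 55% of the time, for a next-assignment hit rate of about 51%. No size is given for the pilot's gastrointestinal excess. The patient randomised just before has only about a month on treatment, when Table 1 is at 300 mg or below and at most one follow-up chemistry panel has been drawn. All of this stands, and it is why the imperfect-inference range is the relevant one.

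It also stands that small blocks serve the purpose Section 6.D.2 states. A reader might infer that a fixed block of 4 offers nothing that varied blocks do not; the imbalance figures show otherwise. Across four strata the worst overall imbalance is 4 × 2 = 8 now, against 12 or 16 with varied sizes.

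Partial safeguards exist: Section 6.I.2 plans to look for baseline differences, and its mixed models adjust for pre-treatment drinking. They may reveal or soften selection, but they do not prevent it.

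The reply does not remove the point. The size is still fixed and printed, and some entry decisions are still discretionary.

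**Conclusion.** The point holds as a modest, avoidable vulnerability in allocation. At 60% to 80% accuracy per earlier arm and shifts of 5 to 10 points, bias is about 0.4 to 3.0 points and type I error about 5.0% to 6.7%. Both inputs are assumptions; the documents give neither. The rate of one patient a month per stratum also assumes an even split.

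A reader might infer that a third of assignments are in fact predictable, or that the comparison is biased. The documents do not support that. One third requires every earlier arm to be known without error, and nothing shows that blinding fails, that staff guess, or that anyone acts on guesses. The 7.1% and 13.5% error rates belong to that limiting case.

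A reader might also infer that site clinical staff hold the list. The documents are silent on custody, and silence does not establish it.

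**What to change.** For any assignments not yet used, replace the single block size in Section 6.D.2 with permuted blocks whose size varies at random (for example 4 and 6, or 4, 6 and 8) within the same strata. Leave the sizes out of the protocol text that sites receive. One sentence saying who generates and holds the list would fill the silence on custody.

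The gain is mainly the removal of certainty; average guessing hardly changes. The cost is regenerating the remaining list and accepting the larger possible imbalance shown above. Sizes 4 and 6 give most of the benefit for the smaller loss of balance. The documents do not show whether any assignments remain. If none do, no change to the list is possible. Strata, eligibility criteria, dosing, endpoint and analysis are unaffected.

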6.D.4. Visits 2-17 (Treatment and End-of-Treatment Visits): Subjects will return weekly for study visits to meet with the research nurse, complete questionnaires, and receive medical management (MM, described below). At study midpoint (i.e., 8 weeks after starting medication), another CBC, and chemistry/electrolyte panel (including a serum GGT), will be obtained. Urine drug screens will be checked weekly, and pregnancy tests (in all females of reproductive potential) are repeated monthly. At the end of week 16 (endpoint), subjects will complete the packet of questionnaires and will be interviewed by the research evaluator concerning their alcohol-related symptomatology using the Alcohol Use Disorders section of the SCID over the past 30 days. Subjects will also be interviewed by the research nurse about their use of concomitant medications, occurrence of adverse events, compliance with the protocol, and their assessment of the effectiveness and acceptability of the treatment procedures. A blood sample for measurement of serum GGT and metabolic labs will be obtained to provide an index of potential hepatic effects and to assess the validity of self-reported drinking. A urine drug screen and urine pregnancy screen (in all females of reproductive potential) will be obtained at this time as well. The nurse and study physician will monitor continuing adverse events to their resolution. Subjects requesting (or clearly needing) additional treatment for alcohol problems are (if clinically indicated) discontinued from the study protocol and referred to local treatment centers. Similarly, at the end of the treatment trial, subjects whose drinking requires continued treatment will be referred for such treatment. All subjects will be asked to complete an end-of-treatment evaluation to facilitate planned intention-to-treat analyses. All subjects will be informed of these procedures prior to study enrollment.

6.D.5. Visit 10b (Stress Lab Session 2): This visit will occur between weeks 8-16 of being on the study medication. The session will use the same audio tapes created for the baseline stress lab and the session will be identical to the baseline stress lab (assessments), with the exception of the randomized order of the presentation of the audio tapes.

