6.D.6. Visit 18 (Tapering Medication Checkup): *This occurs two weeks after the endpoint visit (see TABLE 3 below in section #8).* Study medication will be tapered off over approximately 2 weeks. ZNS (or placebo) will be reduced by 100mg every three days until stopped. Subjects will be asked to return to the clinic 2 weeks after the endpoint assessment to assess successful tapering of study medication.

6.D.7. Three Month Follow-up Visits (Visit 19): Subjects will be asked to return at 3 months after the acute 16 week treatment phase is ended, to assess the enduring effects of medication treatment. They will complete TLFB, measures of mood, quality of life, alcohol use disorder symptoms, health symptoms, and blood will be drawn for biomarkers of alcohol use.

6.E. Study Treatments:

6.E.1. Pharmacotherapy Conditions. The medication will be administered as described above. Subjects who have unacceptable side effects or severe psychological symptoms (e.g., suicidal thoughts strong enough to suggest the subject can't be managed safely in the outpatient setting) will be withdrawn from the study.

Subjects will also be withdrawn from the study if they opt to discontinue it, become pregnant, or violate study rules (e.g., fail to attend two consecutive visits).

6.E.3. Medical Management (MM): This is a manual-based minimal behavioral psychosocial intervention that has been used effectively in previous clinical trials to optimize adherence to medication and treatment goals (12, 68). MM helps patients stay focused on treatment goals and on taking the medication, and will take about 20 minutes per appointment, at each appointment. This intervention will help reinforce treatment goals, and allow for a therapeutic interaction with patients on placebo. MM does not include more intensive therapeutic techniques such as those used in Cognitive Behavioral Therapy (CBT). The use of MM will facilitate the evaluation of the medication effect. We will use a modified version that allows for subjects to have a goal of abstinence or non-hazardous drinking.

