Psychiatric diagnosis. The Structured Clinical Interview for DSM-IV (SCID-I) will be used to classify patients according to the presence or absence of standard psychiatric disorders (73).

(b). Areas Assessed At Intake And During Each Treatment Visit:

Alcohol use patterns. The Time-Line Follow-Back Assessment method (TLFB), (74) will be used to estimate current alcohol consumption and drinking at intake and also weekly during treatment. This interview procedure will provide quantity/frequency of alcohol consumption data for each day during the period prior to the interview. Data on cigarette smoking will also be obtained using the TLFB. The Clinical Global Impression scale (CGI) will be used to assess progress in treatment monthly. The Clinical Institute Withdrawal Assessment (CIWA-Ar) will be used to facilitate assessment of withdrawal, and decisions regarding appropriateness for study entry and continuation with respect to physical dependence will be made based on the judgment of study physicians.

Psychological symptoms. The Beck Depression Inventory is generally regarded as a sensitive, self-report measure of depressive symptoms, and will be administered at each treatment visit to provide a means to monitor symptoms clinically. The Spielberger State Anxiety Inventory will be used to measure anxiety symptoms weekly (75). Suicidal ideation will be assessed at each visit using the Columbia Suicide Severity Rating Scale (76). Subjects with any current symptoms of suicidal ideation will be assessed by a licensed study clinician (i.e., an M.D., or Ph.D. psychologist), and referred immediately for further treatment if necessary. Subjects deemed by study clinicians to be at too high a risk of suicide to be managed in the outpatient setting will be discontinued from the study and referred immediately for treatment. PTSD symptoms will be measured by the Clinician-Administered PTSD Scale for DSM-V (CAPS-5) and the PTSD Checklist for DSM-V (PCL(77)-5). CAPS-5 will be conducted at baseline, week 8, week 16, and follow-up; PCL-5 will be conducted at baseline, weeks 1-16 and follow-up.) (78)

Desire to drink. Desire to drink will be assessed at each treatment visit with the Alcohol Urge Questionnaire (AUQ), (79).

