All secondary outcome analyses will be by intention to treat, a conservative approach that is aimed at avoiding an overestimation of the treatment effect and will include all subjects that take any medication and provide drinking data for at least one week. The use of multilevel repeated measure statistical models may increase the study power and potential to detect a treatment effect. This type of repeated-measures analysis 1) provides missing-data imputation procedures that are both conservative and logical; 2) allows for the measurement of the exact time that a given patient is measured at baseline and follow-up points, which need not be the same among patients; 3) plots and analyzes linear and non-linear time-course functions both overall and for subgroups of patients based on each patient's best estimate linear and non-linear regression line plots. We will use all available data on individuals and thus dropouts provide data until the point of dropout. The best-fitting variance-covariance structure between the repeated measures will be selected based on Schwartz-Bayesian Information Criterion (BIC). We will compare dropout patterns between groups and if there are concerns of informative dropout and/or informative intermittent missing data, we will use pattern mixture models (Hedeker and Gibbons, 1997) to perform sensitivity analyses to our main analyses. Adherence to the medication will be evaluated and factored into the analysis. We will evaluate and compare both medication conditions (placebo, ZNS) for percentage of prescribed pills taken. We do not expect a difference, but if one is found, we can then perform additional analysis on the main outcome variables to estimate treatment effects adjusted for percent pills taken. The number of MM sessions attended will be recorded and analyzed similar to the medication adherence.

The three-month follow up data will be gathered using a retrospective TLFB at the follow-up time point, and will be analyzed using logistic regression for PSNHDD, and either linear mixed models or Hierarchical Linear Modeling (HLM) for other outcomes. We will examine that drinking data between the end of treatment and the three-month time point and use the same outcomes as the main analysis. We will be able to examine for persistent effects of ZNS on drinking behavior and related outcomes. These analyses will include pre-treatment and within-treatment drinking data as covariates to evaluate the post-treatment effects of ZNS.

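### 6.E.1 withdraws subjects from the study for side effects or missed visits, against the continued follow-up promised in 6.I.2, so a reachable subject with no heavy drinking can be scored a PSNHDD failure

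*Combined protocol and SAP*

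**What the plan says.** **Withdrawal.** Section 6.E.1 (Pharmacotherapy Conditions) takes subjects with unacceptable side effects or severe psychological symptoms out of the study. It then adds that subjects will be "withdrawn from the study if they opt to discontinue it, become pregnant, or violate study rules (e.g., fail to attend two consecutive visits"). It does not separate stopping medication from stopping follow-up.

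**Follow-up and scoring.** Section 6.I.2, where PSNHDD is the primary outcome, says: "Patients will be followed irrespective of whether they continue to receive medication treatment, so that analysis will include all data available". The same paragraph says that "dropouts will be considered as having relapsed to heavy drinking".

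**Endpoint contact.** Section 6.D.4 states: "All subjects will be asked to complete an end-of-treatment evaluation to facilitate planned intention-to-treat analyses". Section 6.F.2(b) describes the TLFB as giving "quantity/frequency of alcohol consumption data for each day during the period prior to the interview".

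**Missing data.** For the secondary mixed models, 6.I.2 uses all available data, "thus dropouts provide data until the point of dropout". It continues: "We will compare dropout patterns between groups and if there are concerns of informative dropout and/or informative intermittent missing data", in which case pattern-mixture models serve as sensitivity analyses. The retrospective TLFB at three months is described for "drinking data between the end of treatment and the three-month time point".

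**Power.** Section 6.I.6 puts PSNHDD power above 89% with 80 per group and says that this holds whatever the number of dropouts.

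**The concern.** Site staff act on 6.E.1; the analyst assumes that 6.I.2 was followed. If staff stop collecting data when they withdraw someone, the failure rule turns a gap created by the protocol into a recorded relapse, whatever the subject drank. The missed-visit rule is the clearest case, because a subject who returns after two missed visits could fill the gap in one TLFB interview.

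The consequence depends on who is withdrawn. If withdrawal differs by arm and some withdrawn subjects were not drinking heavily, the PSNHDD comparison partly measures retention. If withdrawal is equal, the treatment difference still shrinks. The planned dropout comparisons (6.I.2, 6.I.3) would show an imbalance, but not how far PSNHDD depends on it.

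**Working it through.** **1. The texts side by side.**
- 6.E.1 ends study participation; 6.I.2 continues it regardless of medication. No sentence limits withdrawal to medication.
- 6.D.4 asks everyone for an end-of-treatment evaluation, so one week-16 interview could in principle cover the window. It is a request, and no look-back is set for someone withdrawn weeks earlier.
- Long recall is already accepted: eligibility in 6.C uses a 90-day TLFB.

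**2. Inputs.** From the documents: 80 per arm (6.D.2), alpha 0.05 (6.I.2), pilot successes 12 and 7 (6.I.6), pilot N = 40 (section 3). Assumed: 20 per pilot arm, giving 60% and 35% (pooled 19/40 = 47.5%); a two-sided test; every dropout rate. An unadjusted chi-square test stands in for the planned logistic regression.

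**3. The plan's power figure.** The pooled-variance formula gives
Φ{[0.25 − 1.96 × √(2 × 0.475 × 0.525/80)] / √[(0.60 × 0.40 + 0.35 × 0.65)/80]} = Φ{(0.25 − 0.1548)/0.0764} = 0.894.
This matches the stated figure of over 89%. Exact enumeration of the chi-square test, used below, gives 0.890.

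**4. Rejection with no true effect.** Observed success in an arm = 0.475 − d × L, where d is the dropout proportion and L is the success rate among withdrawn subjects that is lost to failure scoring. For d = 20% v 30% and L = 0.475, the rates are 0.475 − 0.20 × 0.475 = 0.380 and 0.475 − 0.30 × 0.475 = 0.3325. With no dropout, rejection is 0.048.

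| Dropout | L = 0.475 (no data recovered, same success as others) | L = 0.2375 (half lost) | L = 0.10 (mostly relapse) |
|---|---|---|---|
| 20 v 30 | 0.096 | 0.057 | 0.049 |
| 15 v 30 | 0.153 | 0.070 | 0.051 |
| 10 v 30 | 0.231 | 0.088 | 0.054 |
| 20 v 40 | 0.251 | 0.089 | 0.054 |

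**5. Direction.** In the L = 0.475 column, 95% to 99.7% of rejections go against the arm with more dropout.
- If that arm is ZNS, false findings in favour of ZNS are about 0.096 × (1 − 0.949) = 0.005 at 20 v 30 and below 0.001 at 20 v 40. With no dropout the figure is 0.048/2 = 0.024.
- If it is placebo, the false ZNS-favouring rate is 0.096 × 0.949 = 0.091 at 20 v 30 and 0.251 × 0.997 = 0.250 at 20 v 40.

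**6. Power at 60% v 35%.** Observed rate = true rate × (1 − d × s), where s is the share of withdrawn subjects' successes that is lost. Withdrawn subjects are given their arm's success rate. For ZNS 30% v placebo 15% with s = 0.5, the rates are 0.60 × 0.85 = 0.510 and 0.35 × 0.925 = 0.324, so the difference falls from 25 to 18.6 points.

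| Dropout (ZNS v placebo) | s = 0.2 | s = 0.5 | s = 1 |
|---|---|---|---|
| 30 v 15 | 0.814 | 0.660 | 0.366 |
| 20 v 20 | 0.864 | 0.820 | 0.743 |

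These cases take 60% and 35% as rates before dropouts are scored. If the pilot's 12 and 7 already count dropouts as failures, which 6.I.6 does not say, the losses are partly double-counted.

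**The case against.** The strongest reply is that this is loose wording. The rule sits under study treatments, 6.I.2 states the intent to follow everyone, and 6.D.4 asks all subjects for an endpoint evaluation shortly after describing people discontinued from the protocol. Read together, withdrawal could mean leaving treatment only. That reading is possible, but no sentence says it, and the look-back is still undefined.

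Several further points stand:
- Rewording recovers neither refusals nor unreachable subjects, and a heavy drinking day already recorded in the window settles the outcome. The group that matters is reachable, willing and free of heavy drinking throughout the window; the documents give no basis for its size.
- The large rejection rates need no data recovery and withdrawn subjects who do as well as everyone else.
- Failure scoring is a defensible primary rule, and the mixed model for heavy drinking days is a partial cross-check.
- Specific Aim 1 names drinks per week as the primary measure. This point applies to PSNHDD, the primary outcome in 6.I.2 and 6.I.6.

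A reader might infer from "thus dropouts provide data until the point of dropout" that the plan orders collection to stop at dropout. It does not: the phrase describes how the secondary models use available data.

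**Conclusion.** The conflict is in the current text and should be resolved. Followed literally, 6.E.1 can lose obtainable PSNHDD data and turn that loss into failures. The 6.D.4 evaluation mitigates this only in part.

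The size cannot be fixed, because every dropout rate above is assumed. The effect on type I error runs from negligible (4.9% to 5.4% when withdrawn subjects mostly relapse) to material (9.6% to 25.1% in the worst cases, for dropout gaps of 10 to 20 points).

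Two stronger readings are tempting, and the documents support neither. One is that the plan inflates false efficacy claims for ZNS. That needs higher withdrawal on placebo, which nothing in the documents predicts. Excess ZNS withdrawal is conceivable, since 8.B lists events more common on ZNS than on placebo in epilepsy trials (somnolence 17% v 7%). Sections 3 and 4.B.2, however, report good tolerability, and 4.B.2 few dropouts. With excess ZNS withdrawal, failure scoring is conservative for an efficacy claim; the harm is lost power and an estimate biased against ZNS. The other reading is that the stated power is wrong. It reproduces, and whether it already absorbs dropout depends on how the pilot successes were counted.

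**What to change.** 1. Reword 6.E.1 so that side effects, rule violations and missed visits stop study medication but not TLFB collection, which continues by visit or phone unless the subject withdraws consent.
2. In 6.D.4, set the end-of-treatment TLFB look-back to cover the whole endpoint window for withdrawn subjects.
3. In 6.I.2, score as failures by rule only subjects whose window data remain missing; use recovered data otherwise.

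Optionally, pre-specify one PSNHDD missing-data sensitivity analysis, such as multiple imputation from TLFB up to dropout or a tipping-point table by arm. The pattern-mixture option in 6.I.2 is conditional and sits with the secondary repeated-measures models, so its reach to the logistic model is unclear. This is good practice; its absence is not an error.

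The cost is a protocol clarification and a few extra retrospective TLFB calls. Locators (6.F.2(a)), the endpoint evaluation (6.D.4) and retrospective TLFB (6.I.2) are already planned.
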